Table 5. Rectal biopsies from baseline (pre-dose) and post-dose at times associated with PK and PD sampling (1, 3, 6, 24, 72, and 162 hours)

Product	Post- Dose Hours	N	Grade		Grade Epithelial Denudation		Lamina Propria Hemorrhage	
			Median (IQR)	p value*	Median (IQR)	p value	Median (IQR)	p value
Baseline	pre-dose	21	0.0 (0.0, 1.0)	-	0.0 (0.0, 1.0)	-	1.0 (0.0, 1.0)	-
Α	1-6	21	1.0 (0.0, 1.0)	0.79	0.0 (0.0, 1.0)	1.00	1.0 (0.0, 1.0)	1.00
	24	6	0.5 (0.0, 1.3)	1.00	0.0 (0.0, 2.0)	0.31	1.0 (1.0, 1.0)	0.50
	72	8	0.5 (0.0, 1.0)	1.00	0.0 (0.0, 0.0)	0.63	0.0 (0.5, 1.0)	1.00
	168	6	0.0 (0.0, 0.3)	1.00	0.0 (0.0, 0.3)	1.00	1.0 (0.0, 1.0)	1.00
В	1-6	19	1.0 (0.0, 1.0)	0.31	0.0 (0.0, 0.0)	0.79	1.0 (0.0, 1.0)	0.51
	24	6	1.0 (0.8, 1.0)	0.75	1.0 (0.0, 1.0)	0.50	1.0 (0.0, 1.0)	0.63
	72	8	0.5 (0.0, 1.0)	1.00	0.0 (0.0, 0.0)	1.00	1.0 (0.0, 1.0)	1.00
	168	5	1.0 (0.0, 1.0)	1.00	0.0 (0.0, 0.5)	0.63	1.0 (1.0, 1.0)	1.00
С	1-6	16	0.0 (0.0, 1.0)	0.69	0.0 (0.0, 0.8)	0.59	1.0 (1.0, 1.0)	0.22

24	6	1.0 (1.0, 1.3)	0.63	0.5 (0.0, 1.3)	1.00	1.0 (0.8, 1.0)	0.25
72	6	0.5 (0.0, 1.0)	1.00	0.0 (0.0, 1.0)	1.00	0.5 (0.0, 1.0)	1.00
168	5	0.0 (0.0, 0.5)	1.00	0.0 (0.0, 0.0)	1.00	1.0 (1.0, 1.0)	1.00

*Acceptability*. All three DREAM Products were found acceptable to participants, including Product C, the hypo-osmolar, high dose formulation to be used in this trial. Participants indicated high baseline anticipated likelihood of using the products before receptive anal intercourse for HIV prevention, with 15/17 participants indicating at baseline that they would be likely or very likely to use such products.

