Pre-dose baseline visit tissue biopsies, plasma and blood will be collected to provide comparisons for pre and post dosing in challenge studies and to establish that no oral PrEP is being taken, respectively. After a single dose of the TFV douche (previously referred to as Product C in DREAM-01) we will collect samples at predose, 1, 6, 24, and 72 hours to establish the early rate of increase, peak concentrations, and initial decay of TFV and TFV-DP in all matrices. Plasma and PBMC will be collected from each participant at all of these timepoints. Rectal fluid sampling is partially destructive of local matrix, so, we are planning only two rectal fluid samples per participant in the first 72 hours). Colon tissue biopsies will be collected at each of these times, but each participant will be assigned to only one of these post-dose biopsy times, using a sparse sampling approach and population PK analysis. Aggregate estimates for PK parameters will be used. Non-linear mixed effect modeling will be attempted, but the total sample size may be insufficient to generate robust PK parameter estimates.

Note: Gastrointestinal (GI) sampling procedures for PK/PD assessment (e.g. anoscopy, flexible sigmoidoscopy with biopsy) will not be conducted in participants less than age 18. Participants older than age 18 will be prioritized to undergo GI assessment, but if this adversely impacts accrual feasibility, sample collection may be limited to plasma/PBMC only.

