YMSM will then receive a single dose of TFV douche at the research unit, and, asked to retain the douche without defecation for 5 minutes, if possible. Subsequently, participants will be instructed on how to expel the douche contents. The amount of time that the douche was retained and the volume of expelled effluent will be measured. Post-dose observations and data collection will follow at 1, 6, 24, and 72 hours, using a sparse PK sampling design in which plasma and peripheral blood mononuclear cells (PBMC) are collected at each designated time. Participants are randomized to only one time point for flexible sigmoidoscopy with rectal biopsies at either 1, 6, 24, or 72 hours after dosing (thus, providing 4 subjects at each time point). Anoscopy, with rectal fluid collection will occur pre-dose, 1, 6, 24 or 72 hours after dosing to coincide with the time of each participant's flexible sigmoidoscopy. Microbiome specimens will be collected via anoscopy pre-dose and at 24 hrs post-dose.

Between sampling windows, YMSM will complete a web-survey examining their perceived reactions and comfort using the study douche, factors influencing product use in the future, and comfort with the trial procedures. The survey will be administered after dosing but scheduled not to interfere with other study assessments. Sampling for safety, PK, PD, and acceptability assessments will be collected according to the schedule of events. Phase I Trial participants will complete in an IDI as part of their termination visit.

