### 9.4 Accrual and Sample Size

We expect to screen 48 YMSM willing to participate in the in-person Screening Visit. We derive this estimate based on prior experiences in rectal microbicide trials through the Microbicide Trials Network (MTN). We will need to screen and consent approximately 48 YMSM in-person. Assuming a 1:3 ratio of willingness to enroll in a biomedical clinical trial, we will enroll 16 YMSM (n=8 between the ages of 15-19; n=8 between the ages of 20-24) for the Phase I Safety Trial.

A sample of 16 YMSM enrolled in the DREAM ATN trial will allow for maximal comparability with DREAM-01, which included the same product in 18 adults. Comparing 8 participants of DREAM ATN to counterparts in each arm of DREAM-01 provides 80% power, with 2-sided type I error of 5% to detect a difference of 1.0 standard deviations.

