Pharmacokinetics: To characterize the systemic and compartmental pharmacokinetics of a TFV douche following rectal application, as measured by TFV concentrations in plasma, rectal fluid and rectal mucosal tissue homogenates and cells. Pharmacokinetic parameters will be compared to data from studies using rectal dosing of TFV in DREAM-01 and other oral TFV dosing studies in adults, which also included colorectal biopsies. Pharmacokinetics in blood plasma and PBMCs, colon tissue homogenate and cells, and rectal fluid for the TFV-based douche will be evaluated after rectal administration. The primary analysis will use noncompartmental methods to estimate pharmacokinetic parameters, including peak concentration (Cmax, time to peak concentration ( $T_{max}$ ), area under the matrix concentration-time curve from 0 to infinity ( $0 \rightarrow \infty$ ), and terminal elimination half-life. For sparsely sampled matrices (colon tissue homogenate, colon tissue cells, and rectal fluid), we will use population PK methods to build PK models describing individual PK parameter estimates and typical values for the population along with significant covariates (possibly weight, age, pharmacogenetics, creatinine clearance). Tenfovir and TFV-DP assays will be performed by the Clinical Pharmacology Analytical Laboratory (CPAL) at Hopkins and are validated following FDA bioanalytical guidance and approved by an NIH-cross network Clinical Pharmacology Quality Assurance (CPQA) program before used in clinical studies. Primary PK analyses will be testing for (1) differences in PK measures between the two age groups (Kruskal-Wallis) and (2) comparison with DREAM-01 PK results.

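### The 80% power in Section 9.4 does not describe the primary colon-tissue endpoint, and the plan does not say how the DREAM-01 tissue comparison will account for sampling hour

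*Combined protocol and SAP*

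**What the plan says.** Section 2.2 makes colon MMC TFV-DP between 1 and 72 h the primary PK endpoint. Under the sparse design each participant is biopsied at only one post-dose time, "thus, providing 4 subjects at each time point" (Section 9.1).

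Section 9.4 gives the only power statement for the adult comparison. DREAM-01 is described as a study "which included the same product in 18 adults", and "Comparing 8 participants of DREAM ATN to counterparts in each arm of DREAM-01" is said to be a comparison that "provides 80% power, with 2-sided type I error of 5% to detect a difference of 1.0 standard deviations". Neither the matrix nor the sampling hour is mentioned. The 8 is one age group (15-19 or 20-24) out of 16.

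For sparsely sampled matrices, including colon tissue cells, Section 9.6 says "we will use population PK methods to build PK models describing individual PK parameter estimates and typical values for the population", with covariates that may include age. It then lists two primary PK analyses: a Kruskal-Wallis test between age groups, and a comparison with DREAM-01 results for which no method is stated. Its general tests are Kruskal-Wallis and Wilcoxon, without stratification. The same section wants to know whether tissue TFV-DP differs between age groups. Section 1.7 says that aggregate estimates will be used and warns: "Non-linear mixed effect modeling will be attempted, but the total sample size may be insufficient to generate robust PK parameter estimates".

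**The concern.** The power statement treats each participant as supplying one comparable PK value. For plasma and PBMC that is reasonable, because everyone is sampled at every time. For tissue it is not: two participants biopsied at 1 h and 72 h are not exchangeable, since Section 1.6 describes TFV-DP sustained for about 24 h and then falling by day 3.

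Two things follow. First, 80% is printed for a comparison that may not reach it on the endpoint that matters most for the adult-to-YMSM bridge. Second, the analysis that would remove the hour effect is not tied to that bridge. DREAM-01 also took tissue at 3 h and at about one week, so a comparison that ignores hour could mistake a difference in sampling times for a difference between populations. The age-group test has the same weakness, because Section 3.5 does not say that hours are balanced within age group.

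**Working it through.** **1. The plan's own figure.** Two-sample t-test, difference 1.0 SD, two-sided 5%. Noncentrality = √[n₁n₂/(n₁+n₂)], df = n₁+n₂−2.

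| Comparison | Noncentrality | Power (t) | Power (normal) |
|---|---|---|---|
| 8 v 18 | √(144/26) = 2.353 | 61.7% | 65.3% |
| 8 v 8 | √(64/16) = 2.000 | 46.1% | 51.6% |
| 16 v 18 | √(288/34) = 2.910 | 80.6% | 82.9% |

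The stated 80% does not reproduce with 8 participants. It matches all 16 against 18. A one-sample or paired normal formula with n = 8 also gives 80.7%, but DREAM-01 is a separate cohort, so that form does not apply.

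**2. Tissue values available.** DREAM ATN: 16 participants over 4 hours gives 4 per hour, or about 2 per hour in one age group of 8. DREAM-01 TFV-DP counts per hour are not given, so two assumptions are used:
- A: 18 values split evenly over the four hours (4.5 each).
- B: Table 5 histology counts for Product C as a proxy: 6 at 24 h, 6 at 72 h, and 16 pooled over 1-6 h, taken as about 5 each at 1, 3 and 6 h. The matched hours are then 5, 5, 6, 6.

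**3. Hour-adjusted power.** Linear model with hour as a factor and one common shift of 1.0 within-hour SD. Noncentrality = √[Σ n₁n₂/(n₁+n₂)] over the four hours; df = total values − 5.

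| ATN values per hour | Assumption | Sum | Noncentrality | df | Power |
|---|---|---|---|---|---|
| 2 (one age group) | A | 4 × 9/6.5 = 5.54 | 2.353 | 21 | 61.2% |
| 2 (one age group) | B | 2 × 10/7 + 2 × 12/8 = 5.86 | 2.420 | 25 | 64.3% |
| 3 | B | 2 × 15/8 + 2 × 18/9 = 7.75 | 2.784 | 29 | 76.8% |
| 4 (all 16) | A | 4 × 18/8.5 = 8.47 | 2.910 | 29 | 80.3% |
| 4 (all 16) | B | 2 × 20/9 + 2 × 24/10 = 9.24 | 3.040 | 33 | 83.9% |

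The row with 2 per hour also describes the whole trial if only half of the participants give tissue. That can happen: Sections 1.7 and 3 exclude under-18s from biopsy and allow collection to be limited to plasma and PBMC if accrual suffers.

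The two age groups against each other, 2 v 2 at each hour: sum 4.00, noncentrality 2.000, df 11, power 44.6%.

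**4. What ignoring hour costs.** Simulated unstratified Wilcoxon test at matched hours, all 16 giving tissue, assumption B, true shift 1.0 SD. Power is about 82% with no hour effect, 64% if 72 h values lie 2 within-hour SD lower, and about 50% if they lie 3 SD lower. The size of the drop is assumed; the protocol gives no within-hour SD.

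**5. Individual parameters.** With one post-dose tissue value per DREAM ATN participant, noncompartmental Cmax, AUC or half-life cannot be computed per person. Individual estimates from a population model would lean on the model's typical value, so they are poor input for a rank test. The extent of that shrinkage was not calculated.

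**The case against.** The strongest reply is that the plan already names a method that uses time. Population PK models concentration over the sampling hours, allows covariates, and with aggregate estimates does not depend on per-person values. A joint fit with DREAM-01 is not ruled out. This stands: a reader might infer that the plan has no hour-adjusted analysis, and Section 9.6 does not support that. What is missing is the link from that model to the DREAM-01 comparison, and a fallback.

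A reader might also compare a single hour, 4 v 6, find 27.7% power, and conclude that the trial would miss a 1.0 SD difference about three times in four. Nothing in the plan says DREAM-01 will be tested hour by hour, so that is the power of an unplanned test.

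Nor does sparse sampling in itself cost much power once hour is modelled. Under assumption A, 8 v 18 gives 61.7% ignoring hour and 61.2% adjusted; 16 v 18 gives 80.6% and 80.3%. Most of the shortfall from 80% comes from attaching that figure to 8 participants. The further risks are fewer tissue values and an unadjusted test.

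The DREAM-01 counts are a weak proxy. Table 5 reports histology and shows 16 + 6 + 6 + 5 = 33 Product C values from 18 adults. Even the matched-hour set of 5 + 5 + 6 + 6 = 22 must include repeats, while the calculation treats values as independent. The percentages in this review should therefore not be copied into the protocol.

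Finally, the study calls itself exploratory and its PK objective is to quantify. That lowers the stakes, but Section 9.6 still labels both comparisons as primary PK analyses. Section 9.4 names no matrix, so reading its figure as covering tissue is an inference; no other figure is offered for tissue.

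**Conclusion.** The point holds as one of specification and of a stated figure. For colon MMC TFV-DP, the printed 80% for 8 participants against a DREAM-01 arm is not delivered: about 61% to 64% with hour adjustment, and 62% for 8 v 18 ignoring hour. About 80% to 84% is reachable only if all 16 participants give tissue and hour is modelled. These numbers assume a constant shift and equal SD across hours on the log scale, independent values, and the DREAM-01 counts in assumptions A and B.

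Section 9.6 names a time-based model for tissue but not the joint data, study effect or fallback needed to make the comparison, and its rank tests do not account for hour. The documents do not support describing the planned power as 28%. The change should be made; it does not call the design into question.

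**What to change.** **Section 9.6.** Make both tissue comparisons (DREAM ATN v DREAM-01 Product C, and age group v age group) hour-adjusted:
- Main route: a study effect, or an age-group effect, in a population PK model fitted jointly to both studies.
- Named fallback if that model is not robust: a linear model on log TFV-DP at the matched hours (1, 6, 24, 72) with hour as a factor, and a participant term where DREAM-01 adults contribute repeat values.
- Report a geometric mean ratio with 95% CI beside hour-specific medians.
- Do not apply unstratified rank tests to tissue values, or to individual parameters derived from a single tissue sample.

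**Section 9.4.** Replace the 80% with power for this tissue analysis. Compute it from the actual DREAM-01 Product C TFV-DP counts per hour and a range of DREAM ATN tissue values per hour (4, 3 and 2). State it separately from any plasma or PBMC comparison.

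**Cost.** Protocol wording and a short analysis of data the programme should already hold; no extra samples, visits or participants. Two small downsides: the model assumes a constant log-scale shift over 1 to 72 h, which the hour-specific medians help a reader to judge, and the stated power becomes less favourable.

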# 1.3 Description of TFV Rectal Douche Study Product

We propose a phase I clinical study of a dose of a tenofovir (TFV) enema in YMSM. The douche formulation is selected to provide a more behaviorally congruent pre-exposure prophylaxis alternative to both oral daily dosing and rectal gel dosing using pharmacokinetic and behavioral rationale described above. Unique among rectal microbicide studies and in biomedical HIV prevention trials with youth, we propose this initial single dose study of the TFV douche in order to have sufficient evidence to ensure the inclusion of YMSM if subsequent trials demonstrate HIV prevention efficacy and we are successful in demonstrating PK congruence between adults and YMSM in the colon tissue cell concentrations.

The study product active ingredient is TFV (PMPA,9-[(R)-2-(phosphonomethoxy)propyl] adenine monohydrate), an acyclic nucleotide analogue of adenosine monophosphate. Once inside the cell, TFV is phosphorylated by cellular enzymes to form TFV-DP. TFV-DP is a competitive inhibitor of HIV-1 reverse transcriptase (RT) that terminates the growing deoxyribonucleic acid (DNA) chain. TFV-DP is a weak inhibitor of mammalian DNA polymerases  $\alpha$ ,  $\beta$ , and mitochondrial DNA polymerase. TFV is licensed only as the prodrug form, TFV disoproxil fumarate (TDF) which is available in a 300 mg dosage form as well as in fixed dose combination with emtricitabine (200 mg), also an HIV nucleoside reverse transcriptase inhibitor (NRTI), marketed as TruvadaTM and indicated for prevention of HIV infection in persons at risk of HIV infection as well as for treatment in combination with another NRTI and a more potent antiretroviral drug. TFV Powder will be supplied by CONRAD.

The TFV douche product is a clear, colorless fluid with pH 7.0. It contains 660 mg TFV in 125 mL, and has a hypotonic osmolality (~ 145 mOsm/kg). Characteristics of the formulation of the TFV douche which will be tested clinically are specified below in Table 2.

	Product C
Dosing	660 mg per 125 mL
Concentration	5.28 mg/mL
Ingredients	
TFV	0.66 g
NaOH 18%w/v (18g NaOH in 100 ml water)	0.75 mL
NaCl, NF	0.412 g
Purified water	124.25 g or mL
Target Osmolality	145sm/kg

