# 1.6 Rectal Microbicide Development in the DREAM Program

DREAM ATN has been developed to dovetail with the on-going DREAM clinical development program of a rectal TFV douche described below. The goal of DREAM ATN is to define the safety, PK, PD, and acceptability of a rectal TFV douche administered to adolescent and young adult MSM. Establishing, as we expect, the PK equivalence of the TFV douche in adolescent, young adult, and adult study participants is designed to accelerate inclusion of YMSM in future TFV douche studies and to provide a PK bridge to YMSM once efficacy of the TFV douche is demonstrated in adults, as is anticipated to be the first population studied in pivotal randomized clinical seroconversion studies leading to market approval by FDA. The necessity of extending the testing of new HIV prevention modalities to this proposed adolescent population is motivated by anticipated behavioral differences, not biological ones. The biological differences in existing safety cohort (DREAM-01 with -02 and -03 ongoing) are anticipated to be trivial given the maturation of the GI tract in proposed study participants. We have no expectation of differences in safety or PK readouts in the proposed trial, though capturing these endpoints is essential, nonetheless. The product to be studied in DREAM ATN is the same as that studied in DREAM-01 (completed), DREAM-02 (recruiting), and DREAM-03 (recruiting). For context, these studies are summarized here.

**DREAM-01 (completed)** is the initial clinical study in the DREAM Program and designed as a single ascending dose study to demonstrate safety, acceptability, and feasibility of exceeding pre-established colon tissue cell TFV-DP concentration targets (associated with full protection in iPrEx) for one week. Preliminary results of DREAM-01 indicate that objectives were met or exceeded (details below).

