# 1.7 DREAM ATN Design Rationale

According to our working target product profile and our clinical niche as an on demand PrEP product, the TFV douche is being developed to provide protective concentrations in colon tissue cells for a similar duration as that achieved using the on demand oral F/TDF 2+1+1 regimen demonstrated equally effective with daily F/TDF in Ipergay. Therefore, sampling for PK and safety will occur over 72 hours based on our model-based PK estimates. In addition, we intend to establish the congruence of PK between adult in the DREAM studies and the YMSM population to be recruited in this DREAM ATN protocol. Accordingly, we propose a slightly shorter total PK sampling duration (3 days) when compared to DREAM-01 (7 days). This

will enable documentation of concentrations throughout the first day when DREAM-01 indicated sustained concentrations well above target concentrations in colon tissue cells as well as the initial decay in concentration that occurs between 24 and 72 hours when colon tissue TFV-DP median concentration falls nearer to the 4 dose per day target concentration.

To achieve these goals, blood (plasma and cells), colon tissue (tissue homogenate and cells), and rectal fluid will be collected using a relatively sparse sampling scheme that balances a desire for rich PK data collection and feasibility. Altogether, each participant will have 5 pharmacokinetic blood samples, 2 rectal fluid samples, and 2 biopsy sessions (up to eight pinch biopsies at baseline and 20 pinch biopsies at one time point following dosing) for the enema product studied. The total number of pinch biopsies collected following enema formulation dosing (n=20) in adolescents is well below the number collected in adult participants (n=120) in DREAM-01.

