#### 9.6 Data Analysis

For primary endpoints, sensitivity analyses will be performed by age group (15 to 19-year-old YMSM; 20 to 24-year-old YMSM). PK estimates will be reported overall and per group, given need to examine whether there are significantly different TFV-DP rectal tissue levels across these two age groups. Safety data will be reported in the aggregate for the overall population, as safety is not expected to differ significantly by age group. As noted above, sample size is conditioned to a great degree on having a comparable, complete, and relevant cohort for comparison to DREAM-01. Descriptive statistics and graphics will be used to summarize the characteristics of endpoints across each step of the study. Continuous measures will be summarized by

means and standard deviations or median and interquartile range depending on data distribution. For binomial endpoints, 95% exact confidence intervals will be calculated. Given the small sample size and possible non-normality of the data, non-parametric tests will be used to test for differences among (Kruskal-Wallis) and between (Wilcoxon rank sum test) test formulations.

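### Section 1 aims for PK congruence between YMSM and adults, but the primary PK analyses in 9.6 test for differences, with no ratio, interval or margin that could support it

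*Combined protocol and SAP*

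**What the plan says.** The aim is stated three times in Section 1. Section 1.6 speaks of "Establishing, as we expect, the PK equivalence of the TFV douche in adolescent, young adult, and adult study participants", intended among other things "to provide a PK bridge to YMSM once efficacy of the TFV douche is demonstrated in adults". Section 1.3 locates it in the target tissue: "demonstrating PK congruence between adults and YMSM in the colon tissue cell concentrations". Section 1.7 repeats it: "we intend to establish the congruence of PK between adult in the DREAM studies and the YMSM population".

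The analysis is in 9.6. The pharmacokinetics paragraph ends: "Primary PK analyses will be testing for (1) differences in PK measures between the two age groups (Kruskal-Wallis", "and (2) comparison with DREAM-01 PK results". The second item has no method. Earlier in 9.6, PK is to be reported overall and per age group, "given need to examine whether there are significantly different TFV-DP rectal tissue levels across these two age groups". The general test sentence reads "non-parametric tests will be used to test for differences among (Kruskal-Wallis) and between (Wilcoxon rank sum test) test formulations", although this trial has one formulation. Exact 95% intervals are promised for binomial endpoints only.

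Section 9.4 sizes the DREAM-01 comparison to detect a difference of 1.0 SD. The formal primary PK objective (2.1) is descriptive: to quantify TFV-DP in colonic tissue cells.

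**The concern.** A test of no difference answers a different question from the one Section 1 asks. Rejection would count against congruence. Failure to reject would not count for it, because that result also arises when the data are few or noisy. Section 1.6 says the team expects no difference, so its expected outcome would appear in the planned primary analysis as a non-significant p-value. Nothing in Section 9 says how large a difference between YMSM and adults the data have excluded, and a bridge from adult efficacy needs exactly that. The less informative the data, the easier it is to see no difference.

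**Working it through.** **Plan's own figure.** Section 9.4 states 80% power at two-sided 5% for a 1.0 SD difference, comparing 8 participants with their counterparts in DREAM-01 (18 adults). A two-sample calculation gives 62% (t) or 65% (normal) for 8 v 18, and 46% or 52% for 8 v 8. About 80% appears for 16 v 18 (81% or 83%). Whether the 80% is right is a separate matter. The point here is that the sizing, like the test, is for detecting a difference.

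**Inputs from the documents.** Age groups of 8 and 8, and 18 adults in DREAM-01 (9.4). Plasma and PBMC from every participant at every time; one post-dose biopsy time each, giving 4 per time (9.1). No GI sampling under age 18 (1.7 and 3). Product C histology counts of 6 at 24 h and 6 at 72 h (Table 5).

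**Assumptions.** Log-normal concentrations with common log SD 0.5, 0.8 or 1.0 (none is given); a true ratio of 2, that is a log shift of 0.693; all 16 and all 18 contribute plasma and PBMC; the DREAM-01 tissue PK count per time equals the histology count of 6.

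**Chance of a non-significant result when exposure truly differs twofold** (exact two-sided rank-sum test at 5%, simulated; with two groups, Kruskal-Wallis uses the same ranking). Repeat simulations agree to within about 2 points.

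| Comparison | SD 0.5 | SD 0.8 | SD 1.0 |
|---|---|---|---|
| 8 v 8, age groups, plasma/PBMC | 28% | 64% | 76% |
| 16 v 18, YMSM v DREAM-01, plasma/PBMC | 3% | 34% | 53% |
| 4 v 6, tissue at one time | 60% | 83% | 86% |

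**What an interval would show.** The 90% CI is the estimated ratio multiplied and divided by exp(t × SD × √(1/n₁ + 1/n₂)), with t the 95th percentile on n₁ + n₂ − 2 degrees of freedom. At SD 0.8:

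- 8 v 8: exp(1.761 × 0.8 × 0.500) = 2.02
- 16 v 18: exp(1.694 × 0.8 × 0.344) = 1.59
- 4 v 6: exp(1.860 × 0.8 × 0.645) = 2.61

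**Is congruence reachable?** Take 16 v 18, a true ratio of 1, and two one-sided tests at 5% each. With an illustrative margin of 0.5 to 2.0, power is 99% at a CV of 50%, 76% at 80% and 53% at 100%. With 0.80 to 1.25 it is 40% at a CV of 30% and below 1% at 50% or more. These margins show the range; they are not proposals.

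**Tissue.** The 4 per time requires all 16 participants to be biopsied (16 ÷ 4), so each participant under 18 reduces it. Tissue for the 15 to 19 group can come only from those aged 18 or 19. If 4 per time split 2 v 2 by age, the smallest exact two-sided p is 2/6 = 0.33, so an age test at a single time could not reach 5%.

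**The case against.** The strongest reply is that this is a 16-person exploratory study whose formal PK objective is to quantify. Section 9.1 describes the goal as descriptive, 9.3 says the data may not fully answer the hypotheses, and none of those hypotheses is equivalence. That stands: a reader might infer that equivalence is the trial's single purpose, but it is a Section 1 rationale beside a descriptive objective. It does not remove the mismatch, because 9.6 names tests as the primary PK analyses. If the aim is descriptive, estimates with intervals fit it better than p-values.

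A reader might also infer that the plan does nothing but test for a difference. It does not support that either. Section 9.6 plans noncompartmental parameters, population PK with age as a possible covariate, and estimates per age group. The DREAM-01 comparison is under-specified rather than assigned a wrong test. What is missing is a between-group contrast, its interval and a rule for judging it.

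A third tempting reading is that the sponsor will report a non-significant result as congruence. No passage says so, and for acceptability 9.6 treats non-rejection cautiously. The plan leaves that step open without prescribing it.

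Finally, the sizes rest on assumed SDs, and twofold is an illustrative choice. Section 1.6 reports DREAM-01 colon-cell concentrations more than 10-fold above target, with a smaller excess by 72 h, so whether twofold matters is for the sponsor to argue. That is a reason to state and justify a margin.

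**Conclusion.** The concern holds in this form: Section 1 states a congruence or equivalence aim, and the primary PK analyses in 9.6 cannot support that conclusion, because they test for differences or name no method and specify no ratio, interval or margin.

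The size depends on variability the documents do not give. A missed twofold difference is not the likely result everywhere: for YMSM v DREAM-01 in plasma or PBMC it is the minority outcome at log SD 0.5 and 0.8 and about even at 1.0. It is the likely result for the age groups at SD 0.8 or above, and for tissue at one time at all three SDs. The 8 v 8 and 16 v 18 rows do not describe colon tissue, the primary matrix.

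It would go too far to say the bridging question cannot be answered. The same data can yield ratios and intervals, and with all 16 v 18 and moderate variability a wide margin is reachable. A tight margin is not, and no analysis can supply tissue data for participants under 18.

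**What to change.** In 9.6:

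- Make the primary PK comparison the geometric mean ratio with its 90% CI, for YMSM v DREAM-01 Product C and for the younger v older age group. Give it per time in plasma and PBMC, and pooled over times or from the population model for tissue.
- Keep the rank tests as descriptive.
- State that a non-significant test will not be reported as congruence or equivalence.
- Claim congruence only if the CI lies within a margin that the sponsor fixes and justifies before the ATN PK results are analysed. Otherwise report the ratio and its limits. The study is open-label and DREAM-01 results are already known, so the safeguard is a dated, reasoned margin; blinding cannot provide it.
- State that the tissue comparison includes no participants under 18.

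The cost is SAP wording and one extra table, with no added participants or samples. The downside is that the conclusion, especially for tissue, will probably be weaker than equivalent.
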